4. INVESTIGATIONAL PLAN

4.1. Study Objective(s)

Patients undergoing cardiothoracic surgery ≤ 36 hrs after last apixaban or rivaroxaban dose are at increased risk of bleeding due to the anticoagulant effect of these medications. The DrugSorb-ATR hemoadsorption cartridge removes circulating apixaban and rivaroxaban at rates much higher than normal washout, thus reversing anticoagulation, improving hemostasis, and reducing surgical and early post-surgical blood loss.

The objectives of this study are as follows:

- To demonstrate reductions in surgical and early post-surgical bleeding with the intraoperative use of DrugSorb-ATR in patients undergoing cardiothoracic surgery with CPB ≤ 36 hrs after last apixaban or rivaroxaban dose;
- To demonstrate reductions in circulating apixaban or rivaroxaban blood levels ($\Delta[DOAC]$) with the intraoperative use of DrugSorb-ATR;
- To establish the safety of the intraoperative use of DrugSorb-ATR in the intended population.

The hypothesis is that, for patients undergoing cardiothoracic surgery with CPB ≤ 36 hrs after last apixaban or rivaroxaban dose, the intraoperative use of DrugSorb-ATR will significantly reduce surgical and early post-surgical bleeding as measured by a ranked composite endpoint of clinically meaningful bleeding metrics: 1) fatal bleeding occurring within 48hrs post operation, 2) moderate, severe, or massive bleeding events based on the Universal Definition of Perioperative Bleeding in Cardiac Surgery (UDPB) ≥ 2 classification, and 3) 24-hour chest tube drainage (CTD).

4.2. Study Design

This will be a prospective, multi-center, randomized, double-blind clinical study. Subjects will be randomized in a 1:1 ratio to either standard of care (SOC) or standard of care plus intraoperative treatment with DrugSorb-ATR.

4.3. Study Outcomes

4.3.1. *Primary Effectiveness Endpoint:*

- Ranked composite of surgical and early post-surgical bleeding events:
 - 1) Fatal bleeding events occurring within 48hrs post-index procedure,
 - 2) UDPB ≥ 2 perioperative bleeding, and
 - 3) 24-hour chest tube drainage volume (mL).

Refer to [Table 1](#) for details of the UDPB classification of bleeding events.

4.3.2. *Key Secondary Effectiveness Endpoints:*

- Percent change in pre-CPB vs. post-CPB blood apixaban levels as measured by liquid chromatography/tandem mass spectrometry (i.e., Δ [Apixaban]).
- Percent change in pre-CPB vs. post-CPB blood rivaroxaban levels as measured by liquid chromatography/tandem mass spectrometry (i.e., Δ [Rivaroxaban])

4.3.3. *Additional Secondary Effectiveness Endpoints:*

- 24-hour chest tube drainage volume
- Total platelet transfusions during the index hospitalization (volume and units)
- Total PRBC transfusions during the index hospitalization (volume and units)
- Total UDPB events (by class)
- All surgical re-exploration for excessive bleeding
- Total fatal perioperative bleeding events

4.3.4. *Exploratory Endpoint(s):*

- Area under the concentration time curve (AUC), for intraoperative apixaban or rivaroxaban pharmacokinetic (PK) concentration
- Operative time (measured from start of skin incision to completion of chest closure)
- Duration of ICU stay
- Duration of hospital stay
- 30-day hospital readmissions

4.3.5. *Primary Safety Endpoint:*

- The primary safety endpoint of this trial is to evaluate the product safety profile through the GCP-level assessment of AEs during the study period.

4.3.6. *Additional Safety Endpoints:*

- 30-day cardiac mortality
- 30-day all-cause mortality
- Postoperative stroke during the index hospitalization
- Postoperative myocardial infarction (MI) during the index hospitalization
- Urgent postoperative coronary revascularization during the index hospitalization
- Postoperative venous thromboembolic events (VTE) during the index hospitalization
- Serious device-related adverse events

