9.1. Procedures and Assessments by Study Phase

Subjects are considered enrolled in the study at the time which consent or assent (in the case of a proxy providing permission for an incapacitated subject) to participate in the study is provided. Details on the consent process are provided in [Section 15.3](#) and the ethics of consenting non-vulnerable and vulnerable (incapacitated) populations are detailed in [Appendix 3](#).

[figure not shown]
Subjects who do not meet study entry (inclusion/exclusion) criteria are screening failures and will exit the study. Treated subjects will be followed up through 30 days after the surgical procedure.

The start of the investigation is defined as the date of consent to enroll the first prospective subject. The end of the investigation is defined as the date of the last subject's last contact or assessment (whether scheduled or unscheduled).

The investigation is divided operationally into 6 phases:

- Screening Phase – the period between the time consent/assent is provided for study participation and the start of the surgical procedure with CPB
- Pre-CPB Phase – the period within 2 hours before start of the operation with CPB (time of skin incision). *Note: The Pre-CPB Phase may overlap with the Screening phase.*
- Operation Phase – the start of the surgical procedure (defined as skin incision) until chest closure.
- Post-CPB Phase – the period from the end of CPB up to admission to the Intensive Care Unit (ICU). *Blood sampling for drug removal obtained in the post-CPB phase should be drawn as soon as possible following the end of CPB, and no later than 30min after the subject has been disconnected from the CPB circuit.*
- Post-operation Phase – from admission to the ICU through Day 29 or the point of discharge from hospitalization, whichever is sooner. **Discharge from hospitalization** means the date of initial discharge from the hospital in which the cardiothoracic surgery was completed (i.e., index procedure) irrespective of discharge to home care, secondary care or other rehabilitation unit.
- Day 30 Evaluation Post-Cardiothoracic Surgery – The subject status on postoperative day 30 will be evaluated by telephone contact, in-person follow-up visit, or review of medical records. Assessment of mortality (i.e., vitals status), blood product transfusions, and other adverse events will be performed.

An overview of the investigation design is shown in [Figure 5](#).

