All bleeding events are to be recorded as AE/SAEs by the Investigator or designee. Volume of blood loss and necessary transfusions will be documented in the corresponding eCRFs where applicable. In some cases, these events may contribute to the subject’s UDPB class. [35] Classifications are based on criteria/events occurring within the first postoperative day (as presented in [Table 1](#)) and will be determined based on the relevant data entered within the eCRFs.

Of note, UDPB counts transfusions of PRBCs, platelets, FFP, and Cryoppt beginning at chest closure. While intra-operative transfusions of these blood products prior to chest closure will be documented, they will not be counted as part of the UDPB classification or contribute to the primary endpoint. Preoperative transfusions are not counted in the UDPB classification. Transfusions of PCC and rFVIIa are counted beginning at the start of the procedure for UDPB. [35] Measurement of CTD volume begins at chest closure for UDPB classification. All subjects with events meeting criteria for UDPB classification of moderate, severe, or massive bleeding (Classes 2, 3 or 4) will be referred to the CEC for adjudication of UDPB bleeding class. Bleeding events occurring beyond the first postoperative day (i.e., not eligible for UDPB classification) will be adjudicated by the CEC for clinical severity. Details on the process for adjudication and relevant definitions are provided in the CEC Charter.

Postoperative Ischemic Events:

Postoperative ischemic events occurring during the index hospitalization will be captured as safety

endpoints in this study. This is with the intent of evaluating any potential risk for ischemic rebound in the setting of rapid antithrombotic drug removal. Postoperative ischemic events include myocardial infarction (MI), stroke, and urgent coronary revascularization. Of note, given the occasional complexities of distinguishing ischemic from hemorrhagic stroke (i.e., ischemic with hemorrhagic conversion), *all* postoperative strokes occurring during the index hospitalization will be captured within the safety endpoint.

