All reported safety events occurring within 30 days of the study procedure that meet programmed criteria for cardiac ischemia or stroke will be submitted to the CEC for endpoint adjudication. All coronary revascularization procedures (regardless of open or percutaneous) that occur post-index procedure and during the follow-up period will be adjudicated by the CEC for the potential safety endpoint of *urgent coronary revascularization*. Details on endpoint definitions, adjudication criteria, and all other CEC processes/procedures are detailed in the CEC charter.

Venous Thromboembolic Events:

Postoperative venous thromboembolic events (VTEs) occurring during the index hospitalization will also be captured as safety endpoints in this study. These include clinically significant deep vein thromboses and pulmonary embolism. The intent is to identify any potential risk for thrombotic rebound in the setting of rapid anticoagulant removal.

All reported safety events occurring within 30 days of the study procedure that meet programmed criteria for VTE will be submitted to the CEC for endpoint adjudication. In addition to confirmation of VTE, the events will be evaluated by the CEC for clinical significance. Details on endpoint definitions, adjudication criteria, and all other CEC processes/procedures are detailed in the CEC charter.

Postoperative Mortality or AEs Resulting in Death

All deaths (including AEs resulting in death) that occur within 30 days of the study procedure will be adjudicated by the CEC for endpoint criteria. This includes assessment of the timing and nature of the mortality (cardiac vs. non-cardiac death). *For the purposes of this study, fatal bleeding will be considered a type of cardiac death.* Details on endpoint definitions, adjudication criteria, and all other CEC processes/procedures are detailed in the CEC charter.

Safety Reporting to the FDA

The Sponsor will provide safety reports (of adverse events, including relatedness to the device, severity, outcome/resolution, and all deaths) to the FDA for each set of 20 subjects enrolled. These reports are independent of the required annual reports for all IDEs.

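### The stroke, MI, urgent revascularization and VTE safety endpoints end at hospital discharge, a time the device may change, although the same events are collected and adjudicated to day 30

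*Combined protocol and SAP*

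**What the plan says.** Section 4.3.6 lists seven additional safety endpoints. The two mortality endpoints have a fixed window, for example "30-day all-cause mortality". Four others end with the hospital stay: "Postoperative stroke during the index hospitalization", "Postoperative myocardial infarction (MI) during the index hospitalization", "Urgent postoperative coronary revascularization during the index hospitalization" and "Postoperative venous thromboembolic events (VTE) during the index hospitalization". The synopsis has the same split, and Section 9.2.1 repeats the in-hospital limit for ischemic events and VTE.

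Section 9.1 defines the post-operation phase as running "from admission to the ICU through Day 29 or the point of discharge from hospitalization, whichever is sooner". Discharge counts whatever the destination, so a transfer to secondary care or rehabilitation also ends the stay.

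Collection and adjudication go further. Section 9.2.1 and Table 6 (footnote n) have AEs recorded to the 30-day follow-up. For VTE, Section 9.2.1 says "All reported safety events occurring within 30 days of the study procedure that meet programmed criteria for VTE will be submitted to the CEC". It has a parallel sentence for cardiac ischemia and stroke, and it sends every coronary revascularization during follow-up for adjudication.

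On the purpose of the ischemic endpoints, the same section says "This is with the intent of evaluating any potential risk for ischemic rebound in the setting of rapid antithrombotic drug removal". The VTE endpoint is given the matching purpose of detecting thrombotic rebound.

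Section 11.8 plans AE frequencies and percentages by arm, MedDRA-coded, with device relationship judged by the investigator. It promises listings of safety endpoint data and leaves further detail to the SAP.

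**The concern.** A window that closes at discharge depends on something that happens after randomization. Hospital stay is an exploratory endpoint (Section 4.3.4), and Section 1.3 reports a shorter total stay with the device in the retrospective rivaroxaban series. If the device shortens stay here, its arm is observed for these events for fewer days. Section 11.8 states no adjustment for time at risk, so a simple percentage would then favor the device with no real safety difference.

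The direction matters because these endpoints exist to detect rebound after rapid drug removal. A shorter device-arm stay pushes them toward reassurance. The cut-off also varies with local discharge and transfer practice, and it sets aside events that the CEC has already adjudicated. A non-fatal stroke on day 12 after a day-8 discharge would be adjudicated but would not count toward the stroke endpoint.

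**Working it through.** The plan states no event rate, power or sample size for these endpoints, so there is no figure to reproduce. The check has two parts.

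**1. Windows side by side**

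| Item | Window | Place |
|---|---|---|
| Stroke, MI, urgent revascularization, VTE endpoints | Index hospitalization | 4.3.6, synopsis, 9.2.1 |
| Cardiac and all-cause mortality | 30 days | 4.3.6, synopsis |
| AE recording | Consent to day 30 | 9.2.1, Table 6 |
| CEC: ischemia, stroke, VTE | 30 days | 9.2.1 |
| CEC: coronary revascularization | Follow-up period | 9.2.1 |

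Only the endpoint definition stops at discharge. For revascularization, Section 9.2.1 adjudicates procedures from the whole follow-up period toward an endpoint that Section 4.3.6 limits to the hospital stay. The two need reconciling in any case.

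**2. Size, on assumed inputs**

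From the documents: 57 evaluable subjects per arm (Section 11.1). Assumed: no true device effect; 30-day risk r of 3%, 6% or 10%; every subject in an arm has that arm's mean stay L.

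- Constant hazard: h = -ln(1 - r)/30, and P(counted) = 1 - exp(-hL).
- Early hazard m times higher in days 0-5: base b = -ln(1 - r)/(5m + 25), and P(counted) = 1 - exp(-b[5m + (L - 5)]) for L of at least 5.
- In-hospital risk ratio = P(device)/P(control).

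Example with r = 6% and stays of 10 (control) and 8 (device) days: the constant hazard gives 0.0164/0.0204 = 0.80.

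Risk ratios at r = 6% (true ratio 1.00):

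| Stay, control vs device (days) | Constant hazard | Early hazard x5 | Early hazard x10 |
|---|---|---|---|
| 7 vs 6 | 0.858 | 0.964 | 0.981 |
| 10 vs 8 | 0.802 | 0.934 | 0.964 |
| 10 vs 7 | 0.702 | 0.902 | 0.947 |
| 14 vs 10 | 0.717 | 0.885 | 0.934 |

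Under the constant hazard the ratios barely move between r = 3% and r = 10%.

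Share of 30-day events counted in hospital across these stays: about 20-48% (constant hazard, r = 3-10%), 53-69% (x5) and 69-79% (x10).

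Masking: under a constant hazard with 10 vs 8 days, a true hazard ratio of 1.25 against the device gives 1.25 x 8 = 10 control-equivalent days, so the observed ratio is 1.00.

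In events, under a constant hazard with 10 vs 8 days and 57 per arm, the expected in-hospital counts (control vs device) are 0.58 vs 0.46 at r = 3%, 1.16 vs 0.93 at 6% and 1.97 vs 1.58 at 10%. The shift is about 0.1 to 0.4 events per endpoint.

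With a fixed 30-day window the planned window is the same in both arms. A device with no effect then has an expected ratio of 1.00 whatever the stay, apart from death as a competing event.

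**The case against.** A reader might infer that harm after discharge goes uncounted. The documents do not support that. The primary safety endpoint is all AEs over the study period, recorded to day 30 in both arms. Fatal events enter 30-day mortality, and readmissions are an exploratory endpoint. What Section 11.8 does not commit to is a CEC-adjudicated 30-day count of these four events by arm. Its AE tables rest on MedDRA coding and the investigator's judgment of device relationship.

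A second argument is that rebound is early and device exposure ends with bypass, so an early window is more specific. Section 3 reasons similarly for fatal bleeding, since anticoagulation may resume as early as postoperative day two. This has force, but it supports an early window of fixed length. No section explains why the window should end at discharge.

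Third, ascertainment is weaker after discharge. Subjects are questioned daily in hospital, whereas the day-30 contact may be a telephone call or record review (Sections 9.1 and 9.1.3). Section 9.1.3 describes that contact as a vital-status check, while Section 9.1 adds other AEs. This is a real limitation: a difference in stay could still affect detection under a 30-day window. The follow-up procedure is the same in both blinded arms, though, and the plan already relies on it for day-30 AEs.

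Finally, the endpoints are descriptive and few events are expected. That stands, and it limits the weight of the point.

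**Conclusion.** The point holds as a weakness in how four descriptive safety endpoints are defined. Their window ends at a post-randomization time that treatment may shorten, while data and adjudication already extend to day 30.

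The size is uncertain because the documents give neither stays nor event rates. For assumed stays of 10 vs 8 days and no true effect, the apparent risk ratio is about 0.80 under a constant hazard and about 0.93 to 0.96 if early hazard is 5 to 10 times higher. Two stronger readings are tempting and unsupported:

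- A 20% bias as the expected result: 0.80 is the constant-hazard case on assumed stays, and the bias is small if events cluster early.
- Two thirds of the events lost: stays of 8 to 10 days leave 67-73% of the calendar window outside the endpoint (20/30 to 22/30), but under early clustering more than half of the events still fall in hospital.

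These endpoints carry no hypothesis test, so type I error and power are not affected. The gain is a fairer safety comparison. The change should be made, but the trial's conclusions do not hinge on it.

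**What to change.** - In Section 4.3.6, the synopsis and the ischemic and VTE paragraphs of Section 9.2.1, define the four endpoints as CEC-adjudicated stroke, MI, urgent coronary revascularization and VTE through day 30. This also removes the revascularization mismatch.
- In Section 11.8 and the SAP, commit to tabulating these adjudicated 30-day counts by arm.
- Keep the in-hospital counts alongside as a supportive display, because later events are less specific to rebound and are less closely ascertained.
- Flag events that occur after DOAC resumption. Table 6 already schedules concomitant medications through follow-up.
- Align Section 9.1.3 with Section 9.1, so that the day-30 contact clearly covers adverse events as well as vital status.

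The cost is low: revised wording, one more table column and a flag, with no new visits, data collection or adjudication. The downside is that the 30-day counts inherit the weaker post-discharge ascertainment, which should be stated when they are reported.

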4.4. Subjects and Selection of Study Population

Subjects must meet all inclusion criteria to be eligible to participate in the study. Subjects meeting any of the exclusion criteria are not eligible to participate in the study.

4.4.1. Inclusion Criteria:

1. Males and females aged ≥ 18
2. Written full informed consent
3. Undergoing cardiothoracic surgery with CPB ≤ 36 hours following last dose of apixaban or rivaroxaban.

Only patients taking apixaban or rivaroxaban for one of the following indications are eligible for enrollment: a) reduction of stroke/systemic embolism in nonvalvular atrial fibrillation, or b) initial or extended treatment of venous thromboembolism (VTE), which includes deep vein thrombosis (DVT) and/or pulmonary embolism (PE).

4.4.2. Exclusion Criteria:

1. Cardiothoracic surgery >48 hours after last known dose of apixaban or rivaroxaban
2. Patients on low dose apixaban or rivaroxaban for prophylactic indications (e.g., DVT prophylaxis after hip/knee replacement surgery, or risk reduction of major CV events in patients with CAD/PAD)
3. Heart-lung transplant procedures
4. Procedures for ventricular assist device (i.e., implant or revision of LVAD or RVAD)
5. Any of the below conditions that pose a known risk for increased bleeding:
 - a. Heparin induced thrombocytopenia
 - b. Preoperative platelet count $< 50,000 / \mu\text{L}$
 - c. Hemophilia
 - d. INR ≥ 1.8
6. Prohibited concomitant antithrombotic medications (reference [Appendix 5](#))
7. Acute sickle cell crisis
8. Known allergy to any of the device components
9. Subjects with active (untreated) systemic infection
10. Subjects with a history of major organ transplantation and those currently receiving immunosuppressive medication (corticosteroids excluded) or who are profoundly immune suppressed
11. Women of childbearing potential with a positive pregnancy test performed during the current admission or who are breast-feeding
12. Subjects with life expectancy of <30 days (not inclusive of the critical condition that is requiring the cardiac operation under study for which there is a reasonable expectation that cardiac surgery with the device may prolong life for more than 30 days)
13. Inability to comply with the requirements of the study protocol
14. Treatment with an investigational drug or device within 30 days prior to surgery
15. Subjects with previous enrollment in this trial

4.4.3. Informed Consent & Enrollment Procedures:

Informed consent shall be obtained in writing from the subject, or their legally authorized representative and the process shall be documented before any procedure specific to the clinical

investigation is applied to the subject; additional details are provided in [Appendix 3](#). If during the course of the study assessments, a subject is found not to be eligible for inclusion in the study, the subject or their representative should be notified and the reason for ineligibility documented on the screening log/form.

The general process for obtaining informed consent shall:

- Ensure that the principal investigator or his/her authorized designee conducts the informed consent process
- Include all aspects of the clinical investigation that are relevant to the subject's decision to participate throughout the clinical investigation
- Avoid any coercion or undue improper influence on, or inducement of, the subject to participate
- Not waive or appear to waive the subject's legal rights
- Use native non-technical language that is understandable to the subject
- Provide ample time for the subject to read and understand the Informed Consent Form (ICF) and to consider participation in the clinical investigation
- Include personally dated signatures of the subject and the principal investigator or an authorized designee responsible for conducting the informed consent process;
- Provide the subject with a copy of the signed and dated ICF and any other written information
- Ensure important new information is provided to new and existing subjects throughout the clinical investigation

4.4.4. Subject Withdrawal/Discontinuation:

Investigation subjects may withdraw voluntarily from the research investigation for any reason and at any time during the course of the investigation. Subjects may also be discontinued from the investigation for the following medical or administrative reasons:

- At the request of the Investigator, if he/she feels that the subject can no longer fully comply with the requirements of the study or if any of the study procedures would not be in the best interest of the subject.
- Termination of the study by the Sponsor.
- Non-compliance with CIP procedures.
- The subject is lost to follow-up. A subject will be considered “lost to follow-up” when all the following criteria are met:
 - Failure to complete the 30-day follow-up visit or follow-up telephone call without due cause; and
 - Documentation of three unsuccessful attempts to contact the subject via telephone and/or by certified mail.

If a subject is withdrawn from treatment, the Sponsor will be notified and the date and reason(s) for the withdrawal will be documented in the subject's electronic Case Report Form (eCRF). For subjects who withdraw assent/consent and those withdrawn at the request of the Investigator, details of the reason for withdrawal will be captured to the extent possible. If a subject is withdrawn, efforts will be made to perform all follow-up assessments, if possible. Other procedures may be performed at the Investigator's (or designee's) and/or Sponsor's discretion. The Investigator (or designee) may also request that the subject return for an additional Follow-up Visit. All withdrawn subjects will be followed until resolution of all their AEs or until the unresolved AEs are judged by the Investigator (or designee) to have stabilized.

Subjects who are withdrawn for reasons not related to investigation treatment may be replaced following discussion between the Investigator and the Sponsor. For subjects who withdraw or discontinue at any point prior to completion of the required follow-up period, all available data will be used in the analysis, following the intent-to-treat principle. In cases where analysis criteria are not met, for example for the Per Protocol population, such subjects may not be included in the analysis. Subjects withdrawing or discontinuing early will be summarized as described in **Section 11.8**, and will be flagged in a listing of disposition information that includes reason for early withdrawal/discontinuation.

